6.4.5 Handling of Missing Data

We will conduct missing data analyses in order to differentiate between data that are missing at random (MAR) and data that are missing related to letrozole use. If missing data can be regarded as MAR, multiple imputations may be used. If the MAR assumption is not plausible, sensitivity analyses will be conducted to evaluate the impact of MAR violations on analyses by specifying models for non-ignorable missing data mechanisms.

7 - Trial Administration

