6.2 Assessments

Endometriosis associated symptoms will be evaluated using a survey modeled after the clinical survey developed by the World Endometriosis Research Foundation Endometriosis Phenome and Biobanking Harmonisation Project [10]. The survey will use a visual analog scale (VAS) to quantify pain and symptoms experienced by participants. Participants will complete this survey at their baseline ultrasound appointment for their controlled ovarian hyperstimulation cycle, the day of trigger shot, 3 weeks following egg retrieval, 6 weeks following egg retrieval and 12 weeks following egg retrieval if not pregnant. The first survey will include questions regarding any recent or prior medical or surgical treatment of their

endometriosis. It will also assess baseline use of pain medications for their endometriosis-associated pain. Study participants will be allowed to take acetaminophen when needed (Tylenol, 650 mg tablet) for pain control, but asked to record the number of tablets used.

Secondary outcomes looking at egg and embryo quality and quantity will be assessed using standard embryologists evaluation and grading of all eggs and embryos collected during controlled ovarian hyperstimulation at the University of California Center for Reproductive Health. Embryologist will be blinded to the study participants' assignments to either placebo or control group.

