6.3.1 Study Schedule

M.D. Visit	
 • M.D. to identify patient as potential study participant • M.D. discusses study with patient • M.D. to notify study team if patient interested
Meet Study Team	
 • Discuss study with patient and answer questions • Subject signs study and HIPPA consents • Randomization completed, patient provided medication
Baseline Ultrasound	
 • Completion of survey #1
Stimulation Monitoring	
 • Daily letrozole/placebo starting with first day of stimulation medications • Routine uterine and ovarian ultrasound monitoring every 1-3 days at UCSF CRH • Routine blood draws for hormonal assessment every 1-3 days at UCSF CRH (patients and providers blinded to estradiol levels)
Trigger Shot	
 • Based on routine trigger shot parameters, including mean diameter of largest follicles • Completion of survey #2 • Discontinuation of letrozole/placebo
Oocyte Retrieval	
 • Retrieve all visible follicles • Follicular fluid obtained for hormonal evaluation • Restart letrozole/placebo evening of retrieval and continue daily for 2 weeks
Embryology Lab	
 • Count total number of retrieved oocytes • Count mature oocytes and fertilization rate (if making embryos) • Assess embryo quality using UCSF CRH standard grading criteria

3 Weeks Post Retrieval	
 Completion of survey #3
6 Weeks Post Retrieval	
 Completion of survey #4
12 Weeks Post Retrieval	
 Evaluation of pregnancy status Completion of survey #5
Long-term Follow-up	
 Medical record review for pregnancy outcomes of transferred embryos and additional endometriosis treatment.

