At 3- 6- and 12-weeks post retrieval, participants will be contacted by phone and reminded to complete survey number 3, 4 and 5 respectively. These surveys will be completed at home electronically via a secure RedCap portal.

Long Term Follow Up:

After completion of survey 5 participants will not be contacted again about the study. Their chart will be periodically reviewed to assess pregnancy outcomes from the controlled ovarian hyperstimulation cycle. Treatments they receive related to their diagnosis of endometriosis will also be reviewed.

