6.3.7 Removal of subjects

Participants will be prematurely discontinued from the study if any of the following occurs:

- The participant withdraws consent
- The participant is lost to follow-up
- The participant experiences an untoward event that warrants discontinuation from the study
- The participant develops a health problem and needs treatment that would affect the results of this study
- The study is cancelled for other administrative reasons
- Death of the participant

At the time of premature discontinuation, an off- study form will be completed and no further data collection will occur. Data through the time of enrollment and premature discontinuation will still be used for study purposes.

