7.9 Data or Specimen Storage/Security

Each individual participant who has their medical records reviewed to assess potential eligibility, is approached for recruitment, and/or consented for study participation will have the following information entered on the Study Recruitment Log, which will be maintained in a secure area at the site: name or initials, date of birth, age, sex assigned at birth, race, ethnicity and enrollment status. Individuals that were assessed as ineligible for enrollment will have the reasons for ineligibility recorded. Information collected on the Study Recruitment Log for enrolled participants, excluding names or initials and dates of birth, will be entered in the study-specific database.

For those individuals who were not eligible or did not consent to participate in the study, will have their information recorded only on the Study Recruitment Log. When study accrual ends, project staff will obliterate all names or initials and dates of birth belonging to individuals who did not consent to participate in the study.

Participants will complete all 5 planned surveys directly through RedCap. The data will be secured on the RedCap website with only research staff allowed access to the questionnaire results.

All consent forms will be filed and stored separate from the raw data, in a secured location under double-lock when not in use and with restricted access during work hours and/or when unattended.

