This study will be stopped prior to its completion if: (1) the intervention is associated with adverse effects that call into question the safety of the intervention; (2) difficulty in study recruitment or retention will significantly impact the ability to evaluate the study endpoints; (3) any new information becomes available during the trial that necessitates stopping the trial; or (4) other situations occur that might warrant stopping the trial.

A participant can leave a research study at any time. When withdrawing from the study, the participant should let the research team know that they wish to withdraw. A participant may provide the research team with the reason(s) for leaving the study, but this is not required. The research team may need to have the participant return so that he/she can be monitored for any future adverse effects from the study treatments, procedures or interventions.

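### Section 6.4.5 sets MAR against letrozole-related missingness and makes the MNAR analysis conditional on an untestable judgement, so pain-driven dropout could go without a stress test

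*Combined protocol and SAP*

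**What the plan says.** Section 6.4.5 is the only missing-data text. It has three steps.

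- Missing-data analyses will "differentiate between data that are missing at random (MAR) and data that are missing related to letrozole use".
- If MAR is accepted, multiple imputation is permitted but not required.
- "If the MAR assumption is not plausible, sensitivity analyses will be conducted", using models for non-ignorable mechanisms.

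It gives no criterion for plausibility and no imputation model, and no other section adds a sensitivity analysis that is run regardless.

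Two other sections limit what could inform the judgement. On withdrawal, section 7.12 says: "A participant may provide the research team with the reason(s) for leaving the study, but this is not required". Section 6.3.7 says that after premature discontinuation an off-study form is completed (its content is not described) and "no further data collection will occur".

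On survey 5, section 6.2 schedules it at "12 weeks following egg retrieval if not pregnant". Section 6.3.5 has participants "reminded to complete survey number 3, 4 and 5 respectively", and section 7.9 states "Participants will complete all 5 planned surveys directly through RedCap"; neither mentions pregnancy.

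**The concern.** The two categories in 6.4.5 are not alternatives. MAR is a statement about whether missingness depends on unobserved values, given what was observed. Arm is observed, so dropout related to letrozole alone is MAR given arm. Dropout because of a pain score that was never recorded is MNAR, whether it happens on letrozole, on placebo or equally on both. A check for an association with letrozole can therefore raise an alarm where there is none and stay silent where there is a problem.

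The MNAR models depend on that judgement. The data in hand cannot show whether MAR holds, and the trial may hold little outside information on why women left.

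The primary objective (4.2) is the effect of stimulation on symptoms, read from pain at baseline and at 6 and 12 weeks (5.2.1). Equal dropout in the two arms largely protects a between-arm contrast, but it does not protect a change over time. If women with higher unseen pain are missing, a MAR-imputed rise is understated; if women with lower unseen pain are missing, it is overstated.

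**Working it through.** **Inputs from the documents (6.4.2, 6.4.3.1).** SD 2.5, effect 3 VAS points, power 90%, dropout 20%, alpha 0.05 (two-sided assumed).

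**The plan's own figure.** The normal approximation gives n = 2(1.96 + 1.2816)² × 2.5² / 3² = 14.6 per arm. The t-test version gives 15.6, so 16, and 16 / (1 − 0.20) = 20 per arm, 40 in total. The stated size reproduces. The 20% allowance covers loss of precision only, not bias.

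**Assumptions, because the documents give no figures.** Five surveys with exchangeable correlation ρ of 0.3, 0.5 or 0.7; true change to week 12 of +2; log-odds of dropout rising by 0.5 or 1 per SD of unseen week-12 pain; week-12 score imputed by regression on the four earlier surveys. Each scenario was simulated in a very large sample, so the results show bias and not chance.

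**Step 1: bias in the pre/post change, 20% missing (truth +2.00).**

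| Dropout mechanism | ρ 0.3 | ρ 0.5 | ρ 0.7 |
|---|---|---|---|
| Depends on recorded week-6 pain (MAR) | 2.00 | 2.00 | 2.00 |
| 0.5 log-odds per SD of unseen pain | 1.80 | 1.85 | 1.91 |
| 1 log-odds per SD of unseen pain | 1.64 | 1.73 | 1.83 |
| Same strength, lower-pain women lost | 2.36 | 2.27 | 2.17 |
| Extreme bound: exactly the highest 20% lost | 1.23 | 1.37 | 1.56 |

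The graded shortfall runs from 2 − 1.91 = 0.09 to 2 − 1.64 = 0.36.

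**Step 2: compare with sampling error.** If both endometriosis arms were pooled, which the plan does not specify, 40 × 0.8 = 32 women would complete. SE = 2.5 × √[2(1 − ρ)] / √32 = 0.52, 0.44 and 0.34 for ρ = 0.3, 0.5 and 0.7. The largest graded biases (0.36, 0.27, 0.17) are below one SE at each ρ. The extreme bound (0.77, 0.63, 0.44) is above it.

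**Step 3: letrozole minus placebo (truth −3), imputation by arm.**

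- Dropout depends on arm alone, 10% versus 30%: −3.00, no bias.
- One rule on absolute pain in both arms, 0.5 log-odds: about 25% missing on placebo and 15% on letrozole; estimate −2.92 to −2.96.
- The same rule at 1 log-odds: 28% versus 12%; estimate −2.73 to −2.87.
- The same rule with a true difference of 0: estimate 0.00.

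With 16 completers per arm the SE is 2.5 × √(2/16) = 0.88, so these biases (at most 0.27) are modest.

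**Step 4: what a letrozole-focused check would see.** Section 6.4.5 names no test. As an illustration, a two-sided Fisher's exact test of missingness by arm, 20 per arm, flags 28% versus 12% in about 15% of trials. It flags pain-driven dropout at 20% in both arms in about 2%.

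**Step 5: what a delta analysis would show.** Shift in the mean change = share missing × delta, so at 20% missing a delta of 3 points moves it by 0.20 × 3 = 0.60. With ρ = 0.5 and 32 completers the significance boundary is 2.04 × 0.44 = 0.90. MAR results between 0.90 − 0.60 = 0.30 and 0.90 + 0.60 = 1.50 would therefore change their conclusion within −3 to +3 (0.47 to 1.67 for ρ = 0.3; 0.10 to 1.30 for ρ = 0.7). Between arms the boundary is about 1.81, and a result of −3 tips only when the arm deltas differ by (3 − 1.805) / 0.20 = 5.97 points.

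**The case against.** The third step of 6.4.5 is better than its first. It is not confined to letrozole-related missingness, so an analyst who suspects pain-driven dropout is sent to non-ignorable models. A reader might infer that the plan has no provision for MNAR, or directs that such dropout be treated as MAR. Neither is supported: the text allows that outcome but does not require it.

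The bias is also small against the 3-point effect in 6.4.2. A reader might infer that the letrozole-placebo result is seriously at risk. It is not, under these scenarios: arm-only dropout leaves it unbiased, and a result of −3 is hard to overturn. Much larger distortions can be produced, but they need complete-case tests together with far steeper or more lopsided dropout than was assumed here.

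The pooled pre/post analysis is an assumption, since 6.4.3.1 names only two-sample tests. Leaving without giving a reason is an ordinary participant right, and the long-term chart review of endometriosis treatment (5.1.1, 6.3.5) could shed some light on women who stop answering surveys without being discontinued.

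All of this stands, and it limits the size of the point. It does not repair the false contrast, and it does not make the trigger testable.

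A reader might also count survey 5 missing in pregnancy as pain-driven dropout. That does not follow, because non-collection there would depend on a recorded status. The schedule in 6.3.1 checks pregnancy status just before "Completion of survey #5", so it can be read as consistent with 6.2; the clearer mismatch is with 6.3.5 and 7.9.

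**Conclusion.** The point holds, as a change that should be made rather than a fatal flaw. Section 6.4.5 draws a statistically wrong distinction and makes its only MNAR analysis depend on a judgement that observed data cannot settle.

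Under the assumed dropout models, a true rise of 2 points is understated by 0.1 to 0.4, less than one SE. This matters mainly if the observed pre/post change is small or null, which is a realistic prospect because the background (2.2) describes an earlier cohort with no marked worsening. The between-arm difference is biased only when dropout depends on unseen pain, and then modestly and mainly if dropout differs by arm.

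The sizes rest on the assumed correlations and dropout strengths and, for the SE, on pooling the two endometriosis arms. The defect in the wording rests on none of these. Confidence is medium.

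**What to change.** In 6.4.5:

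1. Replace the contrast with a definition such as: *MAR means that, given the observed data (arm, baseline and earlier VAS scores, and recorded covariates in the imputation model), missingness does not depend on the unobserved pain score.*
2. Make multiple imputation under that model the committed base analysis. Delete the plausibility trigger and always run one delta-adjusted (tipping-point) analysis, by arm and for the pre/post change. Use deltas from at least −3 to +3 VAS points (the effect in 6.4.2), extended until the conclusion changes or the limit of the VAS is reached. The documents do not state the VAS limits, so give them. Section 6.4.3.1 must first name the group and test for the pre/post estimate.

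The delta analysis will not show which mechanism holds; it shows how far the result depends on MAR. The cost is SAP wording and one extra sensitivity table, with no new data or participants. It should be settled before unblinding.

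Separate minor point: reconcile 6.2 with 6.3.5 and 7.9 on whether survey 5 is collected in pregnant women, and report any such non-collection apart from dropout.

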7.1 Ethical Considerations: Informed Consent/Accent and HIPAA Authorization

Consent for participation will occur in-person by trained providers. The purpose of the study will be explained in detail. In addition, the study process, benefits, risk and compensation will be reviewed in detail. Written consent will be obtained using an IRB approved APPOSE Trial and HIPPA consent form.

7.2 Institutional Review Board (IRB) Review

Pending review.

7.3 Subject Confidentiality

We will use REDCap, a browser-based, metadata-driven, Health Insurance Portability and Accountability compliant, electronic data capture software solution and workflow methodology for designing clinical and translational research databases, to collect our data. All pain surveys will also be completed electronically by patients through REDCap. We will use the REDCap installation which is maintained by the San Francisco Coordinating Center (SFCC) and will store the REDCap data on SFCC servers. These servers are maintained behind a firewall in a secure server room; all servers are backed up regularly off-site.

All consent forms will be filed and stored separate from the raw data in a secured location under double-lock when not in use and with restricted access during work hours and/or when unattended.

All research staff involved in the study are certified by UCSF to conduct research on human participants.

7.4 Deviations/Unanticipated Problems

All deviations from the protocol will be submitted to the Institutional Review Board to determine next steps to resolve the unanticipated problems or deviations.

7.5 Data Collection

As described above in section 7.3.

7.6 Data Quality Assurance

Investigators must protect research participants and produce reliable study information. The study physician will work with site staff to facilitate the receipt of data, provide technical assistance as necessary, and meet regularly via telephone or email with the staff person responsible for site-specific quality assurance. Data edits through range checks and field inconsistencies will be built into the database to enable real time correction of key entries and completion errors.

7.7 Study Records

Maintained on RedCap as discussed in section in 7.3.

7.8 Access to Source

Only IRB-approved individuals will have access to stored RedCap data.

7.9 Data or Specimen Storage/Security

Each individual participant who has their medical records reviewed to assess potential eligibility, is approached for recruitment, and/or consented for study participation will have the following information entered on the Study Recruitment Log, which will be maintained in a secure area at the site: name or initials, date of birth, age, sex assigned at birth, race, ethnicity and enrollment status. Individuals that were assessed as ineligible for enrollment will have the reasons for ineligibility recorded. Information collected on the Study Recruitment Log for enrolled participants, excluding names or initials and dates of birth, will be entered in the study-specific database.

For those individuals who were not eligible or did not consent to participate in the study, will have their information recorded only on the Study Recruitment Log. When study accrual ends, project staff will obliterate all names or initials and dates of birth belonging to individuals who did not consent to participate in the study.

Participants will complete all 5 planned surveys directly through RedCap. The data will be secured on the RedCap website with only research staff allowed access to the questionnaire results.

All consent forms will be filed and stored separate from the raw data, in a secured location under double-lock when not in use and with restricted access during work hours and/or when unattended.

7.10 Retention of Records

Refer to section 7.9 above.

7.11 Study Monitoring

We will follow IRB procedure for reporting and managing untoward events. Project staff will record any untoward events experienced by the participants.

7.12 Data Safety Monitoring Plan

There will be a Data Safety Monitoring Board (DSMB) to ensure the safety of the participants and the validity and integrity of the data. The board will meet monthly to review any safety concerns raised by the study. These will include adverse events, breaches of confidentiality, unanticipated problems involving risk to participants or others.

The Data and Safety Monitoring Board, comprised of [name] (Reproductive Endocrinologist) and [name] (Reproductive Endocrinologist), will meet monthly during the study and review any safety violations or concerns generated by patients and study personnel completing the study protocols.

An adverse event (AE) is any untoward medical occurrence in a subject during participation in the clinical study or with use of the experimental agent being studied. An adverse finding can include a sign, symptom, abnormal assessment (laboratory test value, vital signs, electrocardiogram finding, etc.), or any combination of these.

A serious adverse event (SAE) is any adverse event that results in one or more of the following outcomes:

- Death
- A life-threatening event
- Inpatient hospitalization
- A persistent or significant disability/incapacity
- A congenital anomaly or birth defect
- An important medical event based upon appropriate medical judgment

AEs will be labeled according to severity, which is based on their impact on the patient. An AE will be termed "mild" if it does not have a major impact on the patient, "moderate" if it causes the patient some minor inconvenience, and "severe" if it causes a substantial disruption to the patient's well-being

AEs will be categorized according to the likelihood that they are related to the study intervention. Specifically, they will be labeled definitely unrelated, definitely related, probably related, or possibly related to the study intervention. These will be reported to the IRB on an annual basis.

Results on the progress of the study will be reported annually to the IRB and also upon the study completion. The research team will adhere to the UCSF IRB reporting requirements. No interim analysis will be completed as it would decrease the overall power of the study.

This study will be stopped prior to its completion if: (1) the intervention is associated with adverse effects that call into question the safety of the intervention; (2) difficulty in study recruitment or retention will significantly impact the ability to evaluate the study endpoints; (3) any new information becomes available during the trial that necessitates stopping the trial; or (4) other situations occur that might warrant stopping the trial.

A participant can leave a research study at any time. When withdrawing from the study, the participant should let the research team know that they wish to withdraw. A participant may provide the research team with the reason(s) for leaving the study, but this is not required. The research team may need to have the participant return so that he/she can be monitored for any future adverse effects from the study treatments, procedures or interventions.

7.13 Study Modification

All study modifications will be reported to the IRB for approval prior to proceeding.

7.14 Study Discontinuation

This study may be discontinued at any time by the Data and Safety Monitoring Board.

7.15 Study Completion

Study completion is expected to occur in 6 months upon complete accrual of 60 participants. This allows for 12 weeks of follow from the enrollment of the final participant and completion of statistical analyses.

